8.2.2. Visit 2: First study drug course

(As soon as the biologic results of screening are available, no later than 4 weeks after the start of the screening).

The following study procedures will be carried out at the 1st study drug course:

- Before the 1st study drug course (within 24 hours before study drug course)
 - Complete physical examination.
 - Biometric information: weight.
 - Vital signs: temperature, heart rate, systolic and diastolic blood pressure.
 - Baseline neurological status assessment:
 - INCAT disability score (adjusted INCAT disability score will be deduced from reported values).
 - Patient and Investigator CGI-S.
 - MRC-sum-score.
 - Rasch-modified MRC sum score.
 - R-ODS.
 - Grip strength with Martin vigorimeter in both hands.
 - Biological tests in local laboratory:
 - Serum total IgG trough levels.
 - C3 and C4 antigens.
 - Serum reference sample for long term storage.
 - Analysis at centralised laboratory:
 - BAFF.
 - CH50.
 - FcγRIIB.

- AEs assessment.
- Listing of concomitant medication.
- Patient diary verification. If information on the patient's diary is not clear, the Investigator will ask the patient questions. The investigator may annotate the patient's diary but must date and sign the annotations.
- During the course of study drug infusion:
 - Collection of infusion parameters.
 - Vital signs measured 30-45 min and 60-75 min after the beginning of the infusion: temperature, heart rate, systolic and diastolic blood pressure.
 - Listing of concomitant medication if applicable.
 - AEs assessment.
- 30-45 min after the end of study drug infusion:
 - Vital signs: temperature, heart rate, systolic and diastolic blood pressure.
 - AEs assessment.
 - Listing of concomitant medication if applicable.

8.2.3. Visit 3: 96 hours after the end of the first course (+/- 24 hours)

The following study procedures will be carried out:

- Complete physical examination.
- Vital signs: temperature, heart rate, systolic and diastolic blood pressure.
- Biological tests in local laboratory:
 - Haematology:
 - Complete blood count + differentials, Hb, MCV, platelets count.
 - Haptoglobin.
 - Biochemical:
 - Creatininemia, glomerular filtration rate according to MDRD.
 - LDH.
 - Total and free bilirubin (total and free bilirubin (total bilirubin in all patients; if total bilirubin > ULN, free bilirubin will be assessed from the same blood sample, as total bilirubin).
 - C3 and C4 antigens.

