10.2. Assessment of Safety

The Investigator will ensure that all the AEs occurring during the study are identified and documented in the eCRF. The identification of AEs may come from various sources:

- The Investigator or nurse may clinically observe an AE in the patient at hospital.
- The patient may spontaneously report an AE to Investigator or Nurse.
- From baseline to EOS, the patient will have to document on a patient diary any AE that occurs outside the hospital. This diary will be verified at each visit by the investigator. The patient will be sensibilised to report carefully day and time of TAAEs.
- At each visit the patient will be given a general prompt, e.g. “Did you experience any illness or unusual sign or symptom since your last visit?” in order to ensure that no AE has been forgotten.
- Vitals signs, including systolic and diastolic blood pressures (mmHg), heart rate (beats/minute), and body temperature (°C) will be measured before each infusion, during infusion (30-45 min and 60-75 min after the infusion start) and 30-45 minutes after the end of infusion and will be recorded in the eCRF. Weight will also be recorded before each study drug course, as it is used to calculate the quantity of study drug to be infused.
- Biological tests will be performed at the screening, before each study drug course, 4 days after the first study drug course and at the end of study assessment. Clinically significant abnormality in physical examination or biological tests performed at the screening as per study protocol will be regarded as a medical history.
- The Investigator or a Study Nurse will call the patient 4 days after each treatment course in order to collect information about the possible occurrence of an AE after the patient has left the hospital. The purpose of this phone call is to ensure that all the temporally associated AEs (TAAEs) are tracked.
- If a TAAE is reported by the patient during the phone call, the Investigator will ask the patient additional information at the next visit. If relevant; the Investigator will report the TAAE in the eCRF.

It is the responsibility of the Investigator to collect all the relevant information regarding identified AEs.

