3.4. Multiplicity Issues, Subgroup Analysis, Interim Analysis, Blinding and Randomisation

All analyses will be presented according to the following subgroups and overall:

- Ig-naïve patients
- Relapsing Ig-pretreated patients

However, statistical tests will be performed only for the overall population (not by subgroup).

No interim analyses will be performed and no p-value will be calculated for each subgroup separately. Therefore, no adjustment for multiplicity will be needed.

Secondary and exploratory analyses are purely descriptive even if p-values will be presented, therefore no multiplicity issues are present. No p-value will be provided by subgroup.

Summary of TEAEs will also be presented by relevant subgroups (e.g., by age group [<65 years and ≥ 65 years], sex, race [white, non-white and unknown], and BMI [<30 kg/m² and ≥ 30 kg/m²]).

Likewise, blinding and randomisation is not applicable in this single-arm, open-label trial.

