The rate of of drug-related TEAE will be presented by course number and overall. This rate will be calculated as the ratio between the number of TEAEs starting during a course and the overall number of patients treated at the corresponding course.

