A scatter plot of the values at the EOS assessment as well as the minimum and maximum values of each patient during the treatment follow-up against the values at baseline will be prepared for each parameter. The first diagonal will be displayed by a dotted line.

4.7.3. 1.2. Course and infusion level analyses

Descriptive statistics of laboratory parameters at screening, before and 96h after the 1st IMP course, before the start of each subsequent course and at the EOS assessment will be provided for laboratory parameters as well as for the clinical assessment. The change from before first IMP course to 96h after the 1st IMP course as well as to before subsequent courses will be presented as well as the minimum and maximum values of each patient during the complete treatment follow-up. The complete treatment follow-up of maximum and minimum presentations includes all post-baseline assessments, along with any unscheduled assessment results which do not contribute to by visit descriptive summaries. Similarly, shift tables for the clinical assessment will be produced showing the change from before the first IMP course to 96h after the 1st IMP course as well as to before subsequent courses.

A graphical display of the evolution of each laboratory parameter by course will be presented with connected box-and-whisker plots. The number of observations at each visit will be displayed in the graph.

Detection of hemolysis will be evaluated at course level. The number and percentage of course with hemolysis will be displayed by subgroup and overall in accordance with the IVIg-associated hemolysis criteria published by Health Canada ([Health Canada 2009](#)), adapted to the study as follows:

- Drop in hemoglobin by at least 1 g/dL compared to baseline and
- At least one of the two criteria below are met
 - Positive direct Coombs test
 - At least 2 of the following criteria are met (in absence of negative direct Coombs test):
 - * Reticulocyte count increased by at least $50 \times 10^9/L$ compared to baseline
 - * LDH increased by at least 20% compared to baseline
 - * Haptoglobin value is lower than the lower limit of normal (LLN)
 - * Free bilirubin (or total bilirubin if the free bilirubin is not documented) increased compared to baseline and value is greater than the upper limit of normal (ULN)

In the following situations the courses will be excluded from the analysis:

Criterion for hemoglobin value cannot be evaluated/calculated

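### The haemolysis percentage in SAP 4.7.3.1.2 pools course 1, sampled at about 96 hours, with courses 2 to 8, sampled only about 2 to 4 weeks later, and its exclusion rule makes the denominator hard to read

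*SAP*

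**What the plan says.** **Reporting.** SAP 4.7.3.1.2 plans: "Detection of hemolysis will be evaluated at course level. The number and percentage of course with hemolysis will be displayed by subgroup and overall". SAP 3.4 names the main subgroups as Ig-naïve and relapsing Ig-pretreated patients ("All analyses will be presented according to the following subgroups and overall"). No haemolysis result by course number or sampling time is planned.

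**Sampling.** Protocol 10.2 puts biological tests at screening, then "before each study drug course, 4 days after the first study drug course and at the end of study assessment". The SAP's laboratory time points agree: "before and 96h after the 1st IMP course, before the start of each subsequent course and at the EOS assessment". Protocol 8.2.3 includes haemoglobin, haptoglobin, LDH and bilirubin in the 96-hour visit (V3, window 24 hours either side). After later courses the day-4 contact is a telephone call (Protocol 8.2.4 to 8.2.6). Courses are 3 weeks apart, give or take 7 days. Direct Coombs test and reticulocytes are scheduled only at screening and the end-of-study (EOS) visit. At other times they are done only if blood results raise suspicion of haemolysis (Protocol 8.3; SAP 2.6).

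**Case definition.** Haemolysis needs a haemoglobin drop of at least 1 g/dL from baseline. It also needs either a positive Coombs test or, without a negative one, at least two of four criteria (reticulocytes, LDH, haptoglobin, bilirubin). Baseline is the last value before the first course (SAP 4.3). No haematology is scheduled at V2, so in practice this is screening.

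**Exclusions.** A course is dropped if the haemoglobin criterion cannot be evaluated. It is also dropped if there is no Coombs result and either three or four of the four criteria are not evaluable, or one or two are not evaluable and fewer than two of the rest are met.

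**The concern.** A percentage of courses with haemolysis is interpretable only if each course had a similar chance of being found positive. Here course 1 has an early sample and a late one, and courses 2 to 8 have a late one only. The protocol describes IVIg haemolytic reactions as reversible (9.2.1) and lists the 96-hour haematology among its risk-minimisation steps (9.3), so the early sample can be expected to find events that a late one may miss.

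This is also the only criteria-based haemolysis analysis in the trial. SAP 4.10.2 says it was added because the protocol had not defined one, and haemolytic disorders are among the events of special interest in SAP 4.7.2. At stake is whether a reader can tell what the reported figure measures.

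**Working it through.** The plan states no expected haemolysis rate or precision, so there is no figure to reproduce. The check is of the denominator and of what enters the numerator.

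**1. Planned courses.** Safety uses the Total Treated Set, planned at 42 patients, with 1 + 7 = 8 courses each.
- All courses: 42 × 8 = 336.
- Course 1 (96-hour sample and late sample): 42, and 42/336 = 12.5%.
- Courses 2 to 8 (late sample only): 42 × 7 = 294, or 87.5%.
- Late sample: 21 ± 7 days, so about 14 to 28 days after the course.

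**2. What the exclusion rule does.** For courses 1 to 7 without a triggered work-up, Coombs is missing and reticulocytes are not evaluable. One of the four criteria is then not evaluable, so the course is dropped unless at least two of LDH, haptoglobin and bilirubin are met. This applies even when haemoglobin has not fallen. At course 8 both tests are scheduled (EOS), so the course stays in.

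Let q be the share of courses 1 to 7 that meet two of the three. This is an assumption, as the documents give no value. Assume also that all 42 patients receive 8 courses and no work-up is triggered. The expected denominator is 294q + 42.

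| q | Courses 1–7 kept | Denominator | Course 1 share | Course 8 share |
|---|---|---|---|---|
| 5% | 14.7 | 56.7 | 2.1/56.7 = 3.7% | 74.1% |
| 10% | 29.4 | 71.4 | 4.2/71.4 = 5.9% | 58.8% |
| 20% | 58.8 | 100.8 | 8.4/100.8 = 8.3% | 41.7% |

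**3. Effect on a percentage (assumed counts).** Take four haemolysis courses, all at course 1.
- No exclusions: course 1 is 4/42 = 9.5% (95% Clopper-Pearson interval 2.7% to 22.6%); pooled is 4/336 = 1.2% (0.3% to 3.0%).
- Literal exclusions, q = 10%: pooled is 4/71.4 = 5.6%; course 1 alone is 4/4.2 = 95%.
- Literal exclusions, q = 20%: pooled is 4/100.8 = 4.0%; course 1 alone is 4/8.4 = 48%.

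The same four events give pooled figures from 1.2% to 5.6%. Splitting by course without changing the exclusion rule would make the course 1 row meaningless.

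**4. Direction.** If every course stayed in the denominator and late samples found a fraction f of the course 1 rate, the pooled figure would be (1 + 7f)/8 of that rate: 12.5%, 34.4%, 56.3% and 100% for f = 0, 0.25, 0.5 and 1. But haemoglobin is always compared with the value before course 1, so one unresolved drop can count again. If the same four patients counted at courses 1, 2 and 3, the pooled figure would be 12/71.4 = 16.8% with literal exclusions at q = 10%, above the 9.5% for course 1 in step 3. With no exclusions it would be 12/336 = 3.6%, below it.

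**5. Carry-over (assumed recovery).** Suppose a drop of 2 g/dL at day 4 recovers with a 14-day half-time. At day 21 the residual is 2 × 0.5^(17/14) = 0.86 g/dL, which misses the 1 g/dL criterion. If an equal drop follows course 2, the residual at the next late sample is 0.86 × (1 + 0.5^(21/14)) = 0.86 × 1.354 = 1.17 g/dL, which meets it.

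**6. Attribution.** The SAP does not say which sample belongs to which course. Course 1 has two candidates, V3 and V4.

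**The case against.** The strongest objection is that the exclusion rule defeats a simple dilution argument. A course 2 to 7 whose haemolysis had recovered before its only sample is normally dropped, not counted as negative. That stands. A reader might infer that the pooled percentage must be an underestimate, or that early-sampled courses carry 12.5% of the weight. The documents support neither: dropping non-haemolysis courses pushes the figure up, the fixed baseline lets persistent drops recur, and 12.5% is a share of planned courses, not of evaluable ones.

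A reader might also infer that the output will show a fall from course 1 to later courses and be taken for better tolerance of maintenance dosing. The planned haemolysis table makes no such comparison. Any such contrast would also be confounded, because the planned dose at course 1 is twice that of later courses.

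A third tempting step is to extend the point to adverse events, where "The rate of of drug-related TEAE will be presented by course number and overall". Only course 1 has a scheduled examination and laboratory test around day 4, so finding clinically significant laboratory abnormalities does differ there. But the adverse event items in Protocol 9.5.3 include no source of detection. A separate line for events found at V3 could not be derived without manual adjudication.

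Finally, the timing is partly visible elsewhere. Laboratory values and changes at 96 hours are summarised separately, abnormalities and shifts are shown by visit, and both the component values of patients meeting the criteria and the excluded courses are listed. This lowers the stakes of a descriptive analysis with no test attached. None of it gives a haemolysis rate on a common basis.

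**Conclusion.** The point holds as one about mixed ascertainment. The only planned haemolysis percentages, overall and by Ig status, combine one course that has a 96-hour sample with seven that have only a sample about 2 to 4 weeks later. The exclusion rule leaves a denominator that may consist largely of course 8. The sampling facts and the exclusion logic come directly from the documents. The shares (course 1 about 4% to 8%, course 8 about 74% to 42%) rest on the assumed q of 5% to 20%, full completion and no triggered Coombs or reticulocyte tests. Neither the size nor the sign of the distortion can be stated.

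This is an inexpensive improvement to a descriptive safety table. It does not affect the efficacy conclusion. The SAP already has the pattern: exposure in 4.7.1.2 is split into first course, later courses and all courses, and drug-related events are shown by course number.

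**What to change.** In SAP 4.7.3.1.2, on the Total Treated Set, overall and by Ig status:

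1. State which visit's sample belongs to which course.
2. Report (a) course 1 at the 96-hour sample (V3), up to 42 courses; and (b) each course at its late sample (V4 to V11), split into course 1 (up to 42), courses 2 to 8 (up to 294) and all courses (up to 336).
3. Give the evaluable and excluded course counts in every row.
4. Count a course with an evaluable haemoglobin drop below 1 g/dL as negative, whatever other tests are missing. The drop is a necessary criterion, so such a course cannot meet the definition. Without this change the split does not help.
5. Footnote that (b) can miss transient haemolysis, that a persistent drop can count at more than one course because baseline is fixed, and that the different planned dose at course 1 means the split cannot separate dose from sampling time.
6. Under the by-course table of drug-related events, add a footnote that only course 1 has a scheduled test and examination at about day 4. No separate line is needed.

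The cost is SAP wording and a few table rows, with no new samples or visits. The downside is a longer table with small numbers in the course 1 rows: 4 of 42 would carry an interval of 2.7% to 22.6%.

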8.3. At any course

In case of suspected clinical venous thrombosis: D-Dimers testing will be performed.

In case of suspected haemolysis based on biological tests (Hb, haptoglobin, LDH, total and free bilirubin levels (total bilirubin in all patients; if total bilirubin > ULN, free bilirubin will be assessed from the same blood sample, as total bilirubin)): Reticulocytes and direct Coombs test will be performed.

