To minimize the risk of thromboembolic events, patients with a history of venous thromboembolic disease, myocardial infarction or cerebrovascular accident will be excluded. As well, patients with uncontrolled cardiac arrhythmia and patients with unstable ischemic heart disease will not be allowed to participate to the study.

Acute renal failure

Cases of acute renal failure have been reported in patients receiving IVIg therapy. In most cases, risk factors have been identified. These included pre-existing renal insufficiency, diabetes mellitus, hypovolaemia, overweight, concomitant nephrotoxic medicinal products and age over 65.

To minimize the risk of acute renal failure, patients with a chronic kidney disease (CKD) defined as abnormalities of kidney structure or function, present for >3 months, with implications for health, i.e. patients with persistent albuminuria category A3 and/or GFR <60 mL/min/1.73m² (measured according to the MDRD calculation) will be excluded [39].

The use of loop diuretics is also not allowed if used within 24 hours prior to study drug administration.

Aseptic meningitis syndrome (AMS)

Aseptic meningitis syndrome has been reported to occur in association with IVIg treatment.

Discontinuation of IVIg treatment has resulted in remission of AMS within several days without sequelae. AMS may occur more frequently in association with high-dose of IVIGs.

Haemolytic anaemia

IVIg products can contain blood group antibodies which may act as haemolysins and induce in vivo coating of red blood cells with immunoglobulin, causing a positive direct antiglobulin reaction (Coombs' test) and, rarely, haemolysis. Haemolytic anaemia can develop subsequent to IVIg therapy due to enhanced red blood cells (RBC) sequestration.

Haptoglobin and LDH levels in patients will be assessed at every visit.

Interference with serological testing

After injection of immunoglobulin the transitory rise of various passively transferred antibodies in the patient's blood may result in misleading positive results in serological testing.

Passive transmission of antibodies to erythrocyte antigens, e.g. A, B, D may interfere with some serological tests for red cell antibodies for example the direct antiglobulin test (DAT), direct Coombs' test.

Interaction with other medicinal products

I10E may impair the efficacy of live attenuated virus vaccines for a period of up to 3 months. In the case of measles, this impairment may persist for up to 1 year.

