2.6. Study Plan Table

	Screening	First study drug administration	Day 4 after last infusion at V2	Week 3	Week 6	Week 9	Week 12	Week 15	Week 18	Week 21	End of study visit
	VISIT 1	VISIT 2	VISIT 3	VISIT 4	VISIT 5	VISIT 6	VISIT 7	VISIT 8	VISIT 9	VISIT 10	VISIT 11
Informed consent (before any procedure of study)	X										
Inclusion/exclusion criteria verification	X	X									
Demographics & Medical history	X										
Safety											
Adverse events assessment	X	X	X	X	X	X	X	X	X	X	X
Phone call 4 days (+/- 1 day) after study drug administration				X	X	X	X	X	X	X	
Concomitant medications	X	X	X	X	X	X	X	X	X	X	X
Patient diary (delivery and verification)	X	X	X	X	X	X	X	X	X	X	X
Clinical assessments / Before study drug administration											
Complete physical examination	X	X	X								X
Clinical examination focused on arterial or venous thromboembolic signs				X	X	X	X	X	X	X	
Weight, Body temperature, heart rate, arterial blood pressure (systolic and diastolic)	X	X	X	X	X	X	X	X	X	X	X
Efficacy assessments / Before study drug administration											
INCAT disability score	X	X		X	X	X	X	X	X	X	X
MRC sum-score, Rash modified MRC sum-score R-ODS Grip Strength (both hands)		X					X				X
Patient and Investigator: CGI (Severity)		X					X				X
Patient and Investigator: CGI (Efficacy), CGI (Improvement)							X				X

Biological test Local lab / Before study drug administration	VISIT 1	VISIT 2	VISIT 3	VISIT 4	VISIT 5	VISIT 6	VISIT 7	VISIT 8	VISIT 9	VISIT 10	VISIT 11
Serum Total IgG trough levels		X		X	X	X	X	X	X	X	X
HbA1c (only for patients with a known history of diabetes mellitus), serum IgA levels	X										
Urine protein reagent strip test	X ^a		X ^b	X ^b	X ^b	X ^b	X ^b	X ^b	X ^b	X ^b	X ^b
Urine Pregnancy test for female of child bearing potential	X										X
C3 and C4 antigens		X	X	X							X
Anti HBs & anti HBc Ab, HBs Ag tests, HIV and HCV tests	X										X
Complete blood count and differentials, Hemoglobin, Mean corpuscular volume, platelet count, haptoglobin, LDH	X		X	X	X	X	X	X	X	X	X
Reticulocytes, direct Coombs test, total serum protein level	X										X
AST, ALT, γ GT, ALP	X										X
Creatininemia, GFR ^c , total and free bilirubin ^d	X		X	X	X	X	X	X	X	X	X
Serum reference sample for long term storage		X									X
Biological test Local lab in case of suspected clinical thrombosis											
D-Dimers		X	X	X	X	X	X	X	X	X	X
Biological test Local lab in case of suspected hemolysis											
Reticulocytes, direct Coombs test		X	X	X	X	X	X	X	X	X	X

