Criterion for hemoglobin is evaluable, direct Coombs test neither positive or negative (missing or not-done) and

- 3 or 4 out of 4 criteria (Reticulocytes, LDH, Haptoglobin, free/total bilirubin) cannot be evaluated/calculated or
- 1 or 2 out of 4 criteria (Reticulocytes, LDH, Haptoglobin, free/total bilirubin) cannot be evaluated/calculated and less than two of the remaining criteria are met

A listing of all hemoglobin, reticulocytes, LDH, haptoglobin and bilirubin values will be provided for patients with at least one blood sample for which the aforementioned criteria for hemolysis is met. A listing of the excluded courses will be also given.

All abnormalities, clinically significant or not, will be listed. Pregnancy status and test results will also be listed, including the method of contraception used (if any).

4.7.3. 2. *Vital signs*

Vital signs parameters including systolic and diastolic blood pressure (mmHg), heart rate (bpm), weight, and body temperature (°C) (calculated value according to the way the temperature was measured) will be summarized.

4.7.3. 2.1. Patient level analyses

Descriptive statistics of vital sign values will be presented for the following time points:

- a) Screening
- b) Before the 1st IMP infusion
- c) 30-45 min and 60-75 min after the start of the first infusion
- d) 30-45 min after the end of the first infusion
- e) 96h after the end of the 1st course
- f) EOS

Change from time point b) will be presented for time points c) to e). The minimum and maximum of each parameter during the patient's complete treatment follow-up will be presented. The complete treatment follow-up of maximum and minimum presentations includes all post-baseline assessments, along with unscheduled assessment results which do not contribute to by visit and by timepoint descriptive summaries.

A scatter plot of the values at the end of study assessment as well as the minimum and maximum values of each patient during the treatment follow-up against the values at baseline will be prepared for each parameter. The first diagonal will be displayed by a dotted line.

4.7.3. 2.2. Course and infusion level analyses

Descriptive statistics of vital sign values will be presented at the following time points:

- a) Before the start of the course (only first infusion of a course)
- b) 30-45 min and 60-75 min after the start of the infusion
- c) 30-45 min after the end of the infusion

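### The haemolysis percentage depends on whether a Coombs test was done: tested and untested courses follow different effective definitions, and most uneventful untested courses leave the denominator

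*SAP*

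**What the plan says.** **Definition (SAP 4.7.3.1.2).** The entry condition is "Drop in hemoglobin by at least 1 g/dL compared to baseline and". One of two routes must then be met. The first is a positive direct Coombs test. The second is the marker route, "At least 2 of the following criteria are met (in absence of negative direct Coombs test", where the four criteria are reticulocytes, LDH, haptoglobin and bilirubin. A negative Coombs closes the marker route; a Coombs that was not done leaves it open.

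**Exclusions (same section).** A course leaves the analysis if Hb cannot be evaluated. It also leaves if Hb is evaluable with "direct Coombs test neither positive or negative (missing or not-done) and" either three or four of the four criteria not evaluable, or one or two not evaluable and fewer than two of the rest met. This rule does not ask whether Hb fell.

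**Output.** The number and percentage of courses with haemolysis are shown by subgroup and overall. There is no split by course number or by whether Coombs was done. The excluded courses are listed.

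**Test schedule.** The row "Reticulocytes, direct Coombs test, total serum protein level" in SAP 2.6 is marked at screening and EOS only. A second row, "Biological test Local lab in case of suspected hemolysis", covers Visits 2 to 11. Protocol 8.3 sets the trigger, "In case of suspected haemolysis based on biological tests" (Hb, haptoglobin, LDH, bilirubin), and the action, "Reticulocytes and direct Coombs test will be performed". It gives no numerical threshold. EOS falls three weeks after course 8, or within 7 days of early discontinuation (Protocol 8.2.7).

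**The concern.** The case definition was written for a full set of tests, but the schedule supplies that set routinely only at EOS. SAP 4.10.2 states that the haemolysis analysis was added because the protocol had not defined one, so the criteria were laid over a schedule not built for them.

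Two things follow. Two courses with the same Hb, LDH, haptoglobin and bilirubin values can be classed differently because one had a Coombs result and the other did not. And because reticulocytes are missing at every untested course, the exclusion rule applies to all of them, so courses where nothing happened tend to be removed.

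Haemolysis is a named risk of the product class (Protocol 9.2.1) and one of the significant adverse event groups in SAP 4.7.2. If the SAP is followed exactly, the headline percentage for it reflects testing practice as well as risk, and cannot be read as the proportion of treated courses affected.

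**Working it through.** The documents state no expected haemolysis rate, so there is no figure to reproduce. The check takes the rule through its outcomes and then sizes the effect on stated assumptions.

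**1. Classification by testing status.** "Untested" means Coombs and reticulocytes not done; LDH, haptoglobin and bilirubin are available.

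| Hb drop | LDH/haptoglobin/bilirubin criteria met | Untested | Tested, Coombs positive | Tested, Coombs negative |
|---|---|---|---|---|
| yes | 2 or 3 | haemolysis | haemolysis | no haemolysis |
| yes | 0 or 1 | excluded | haemolysis | no haemolysis |
| no | 2 or 3 | no haemolysis | no haemolysis | no haemolysis |
| no | 0 or 1 | excluded | no haemolysis | no haemolysis |

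With both tests done and an Hb drop, all 16 patterns of the four markers give haemolysis if Coombs is positive, and all 16 give no haemolysis if it is negative. The markers play no part. In an untested course with an Hb drop, "no haemolysis" cannot occur: the course is either a case or excluded.

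**2. Number of courses.** Protocol 12.3 plans 42 patients and Protocol 3.1.4 gives 8 courses. Full exposure is 42 × 8 = 336 courses, of which 42 × 7 = 294 (87.5%) have no routine Coombs and 42 (12.5%) do.

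**3. Illustration.** Assumptions, none from the documents: the same rates in every course; Hb drop 20%; LDH, haptoglobin and bilirubin criteria met in 10%, 8% and 5%, independent of each other and of Hb; Coombs positive in 5% to 40%, independent of Hb; no suspicion-triggered tests.

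- P(at least 2 of 3 markers) = 0.10×0.08 + 0.10×0.05 + 0.08×0.05 − 2×(0.10×0.08×0.05) = 0.017 − 0.0008 = 0.0162.
- Untested courses kept: 294 × 0.0162 = 4.76. Cases among them: 4.76 × 0.20 = 0.95, a rate of 20%.
- Tested courses: all 42 kept. Cases: 42 × 0.20 × 0.05 = 0.42, up to 42 × 0.20 × 0.40 = 3.36, a rate of 1% to 8%.
- SAP percentage: (0.95 + 0.42)/(4.76 + 42) = 2.9%, up to (0.95 + 3.36)/46.76 = 9.2%.
- Same cases over all courses: 1.37/336 = 0.4%, up to 4.31/336 = 1.3%.

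**4. Other assumptions.** The markers are unlikely to be independent of each other or of Hb. Suppose instead that a given share of untested courses meets at least two markers, that most of those have the Hb drop, and that the tested courses have their own case rate:

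| At least 2 markers | Hb drop among these | Tested case rate | Untested kept | SAP percentage | Over all 336 |
|---|---|---|---|---|---|
| 2% | 90% | 2% | 5.9 | 12.8% | 1.8% |
| 5% | 60% | 3% | 14.7 | 17.8% | 3.0% |
| 10% | 50% | 5% | 29.4 | 23.5% | 5.0% |

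The levels move with the assumptions. The loss of most untested courses does not.

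**5. Effect of keeping courses without an Hb drop.** On the step 3 rates, untested courses kept become 294 × (0.80 + 0.20 × 0.0162) = 236.2. The pooled percentage becomes 1.37/278.2 = 0.5%, up to 4.31/278.2 = 1.6%. This one change removes most of the inflation; the difference in definition remains.

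**The case against.** **Suspicion testing narrows the gap.** Protocol 8.3 requires both tests when Hb, haptoglobin, LDH or bilirubin raise suspicion. A course with an Hb drop and two abnormal markers would probably be tested and then judged exactly as at EOS. This stands for the difference in definition, although without a threshold the remaining gap cannot be sized. It does not help the denominator: an uneventful course gives nothing to suspect, stays untested and is excluded.

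**Course 8 against courses 1 to 7.** A reader might infer that the split is by course number. The documents do not support that. Suspected courses can be tested at any visit, and early discontinuers have EOS after an earlier course. The line runs between tested and untested courses.

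**Haemolysis looking several-fold commoner at the last course.** A reader might set 1% to 8% at course 8 against 0.20 × 0.0162 = 0.3% earlier, roughly 3 to 25 times higher. That divides the untested cases by all courses, which the SAP does not do. After its exclusions the untested rate in the same illustration is 20%, so the direction reverses. No display of haemolysis by course number is planned in any case.

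**Coombs positivity.** Protocol 9.2.1 warns that "Passive transmission of antibodies to erythrocyte antigens, e.g. A, B, D may interfere with some serological tests", and names the direct Coombs test. A reader might conclude that only a conversion from negative at screening should count. An Hb drop is still required, so passive positivity alone makes no case. Whether the published Health Canada criteria require conversion cannot be checked from these documents.

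**Mitigation.** Excluded courses and all data are listed (SAP 4.7.3.1.2 and 5.1), and the endpoint is descriptive. Testing status could be recovered from the listings, but the summary percentage would still mislead.

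**Conclusion.** The point holds as one about testing status. Classification and inclusion of a course both depend on whether Coombs and reticulocytes were done, and the SAP pools the results into one percentage. This follows from the documents without assumptions.

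Its size cannot be fixed from the documents. In the step 3 illustration the SAP percentage is about seven times the proportion of all 336 courses (2.9% against 0.4%; 9.2% against 1.3%). In the step 4 scenarios it is about five to seven times (23.5% against 5.0%; 12.8% against 1.8%). These figures rest on assumed rates, full exposure of 42 patients and no suspicion-triggered testing; such testing would change the case counts.

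The primary efficacy analysis is not affected. The change is still worth making before the analysis, because the output summarises a recognised safety risk. The documents do not support replacing the adapted published definition outright or requiring Coombs conversion.

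**What to change.** In SAP 4.7.3.1.2:

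1. Keep the full adapted Health Canada definition, but report it separately for courses with and without a Coombs result, and also with all treated courses as the denominator.
2. Do not exclude a course with an evaluable Hb and no Hb drop. Count it as no haemolysis, since the entry condition has failed whatever the other tests show.
3. Add a row for a common-test definition: an Hb drop of the size already specified plus at least two of LDH, haptoglobin and bilirubin. Judge evaluability on those tests alone, so that a missing Coombs or reticulocyte result does not exclude a course.
4. Optionally, flag whether a positive Coombs was already positive at screening.

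This needs SAP wording and one or two extra table rows, with no new tests or visits. The common-test row is less specific than the published definition, because it can count a course whose Coombs was negative. That is why it should stand beside the full definition and not replace it.
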